**Table 2: Handling Rules of the Analysis Populations for Special Situations**

Situation	Rule for ITT Population	Rule for all Other Populations
Screen failures	Excluded	Excluded
Not receiving treatment	Included	Excluded
Subject enrolled into the study more than once	Only include first enrollment	Only include first enrollment
Subject enrolled in another interventional contraceptive study	Included	Excluded

Screen failures and the 2nd enrollment for a subject will be excluded from all tables and listings except for the data listing which is specifically designed to list these subjects. However, rescreening will be allowed for this study.

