9.3 Analysis Populations

The following subject populations will be created:

- Intent-to-treat (ITT): All subjects enrolled into the study.
- Safety population: ITT subjects who administer the study drug at least once
- Modified intent-to-treat (MITT): Subjects must meet requirements 1, 2, and 3 simultaneously, and at least one of requirement 4 or requirement 5 to be included in the MITT analysis population:

- 1. Between 18 to 35 years of age (inclusive) at enrollment
- 2. Had at least one report of pregnancy status after being enrolled; subjects with a positive serum pregnancy test at enrollment will not be included.
- 3. ITT subjects whose diaries indicate they had at least one episode of coitus while using the study drug (also referred as "Typical-Use")
- 4. Had at least one cycle of eDiary without any backup contraception or EC
- 5. Became pregnant and the pregnancy had a conception date that occurred between enrollment and <8 days after final study drug use
- Efficacy-evaluable (EE): A subset of the MITT population that includes only those subjects whose diaries indicate that they used the study drug correctly for every act of intercourse for at least one menstrual cycle (also referred as "Perfect-Use" or "Per Protocol"). Cycles in which the study drug was used incorrectly for one or more coital acts will be removed, and the correct use cycles will be compressed to provide contiguous cycles of correct use.

The MITT is the primary population for analysis of efficacy. Analyses in the EE population will be considered exploratory only.

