### 4.3 Analysis Populations

Intent-To-Treat (ITT): all subjects enrolled into the study.

Safety Population: ITT subjects who use at least one application of the study product.

Modified Intent-To-Treat (MITT): Subjects must meet requirements 1, 2, and 3 simultaneously and at least one of 4 or 5 to be included in MITT:

1. between 18 to 35 years of age (inclusive) at enrollment
2. at least one report of pregnancy after being enrolled (subjects with a positive serum pregnancy test at enrollment will not be included in the MITT population).
3. ITT subjects whose diaries indicate they had at least one episode of coitus while using the assigned study product (also referred as "Typical-Use")
4. have at least 1 cycle without any backup contraception or emergency contraception (EC) recorded in the eDiary product use questionnaire
5. became pregnant and the pregnancy had a conception date that occurred after enrollment and within 7 days of the date of last dose of study product.

Efficacy Evaluable (EE): a subset of the MITT population that includes only those subjects whose diaries indicate that they used the study product correctly for every intercourse for at least one menstrual cycle (also referred as "Perfect-Use" or "Per Protocol"). Cycles in which the study product was used incorrectly for one or more coital acts will be removed, and the correct use cycles will be compressed to provide contiguous cycles of correct use.

The Table 2 provides the handling rules of the analysis populations for special situations.

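### SAP Table 2 removes treated women who co-enrolled in another contraceptive study from the Safety population, against the Safety definition in both documents, and keeps adverse events from a treated second enrollment out of the safety outputs

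*SAP*

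**What the plan says.** SAP 4.3 builds its populations from "Intent-To-Treat (ITT): all subjects enrolled into the study". It then gives "Safety Population: ITT subjects who use at least one application of the study product". Protocol 9.3 has the same rule: "Safety population: ITT subjects who administer the study drug at least once". Neither definition makes an exception for co-enrollment or repeat enrollment.

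Table 2 of the SAP, also in section 4.3, adds rules for special situations. It has one column for ITT and one headed "Rule for all Other Populations". Two rows matter here:

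- "Subject enrolled in another interventional contraceptive study": included in ITT, excluded from the rest.
- "Subject enrolled into the study more than once": only the first enrollment is kept, in both columns.

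The sentence below the table says that a second "enrollment for a subject will be excluded from all tables and listings except for the data listing which is specifically designed to list these subjects".

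SAP 4.8 runs all safety analyses on the Safety population, and Protocol 9.9 does the same for all safety summaries.

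**The concern.** A woman who applied the gel was exposed to it whether or not she was also in another study. Inclusion criterion 11 asks subjects not to join other clinical studies, so co-enrollment is a departure from the protocol. It does not undo exposure, and under the stated definition it does not take her out of Safety. Table 2 does take her out. A programmer therefore has two conflicting rules for the same woman, and the one in the table removes her adverse events and exposure from the main safety outputs.

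The repeat-enrollment rule raises a related reporting question. If a woman used the gel during a second enrollment, nothing in the SAP says where her adverse events from that period are summarised.

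Adverse events and pregnancy outcomes are secondary endpoints, and both are tabulated on the Safety population. If the conflict is left in place, the choice of rule may be made when the affected women's events are already known.

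**Working it through.** No stated sample size, power or error rate depends on this point, so there is no planned figure to reproduce. The check compares the texts and traces the outputs. A calculation for scale follows.

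**1. Does the second column cover Safety?** SAP 4.3 defines four populations: ITT, Safety, MITT and EE. With ITT in its own column, the other column covers the remaining three. The row for women not receiving treatment (included in ITT, excluded elsewhere) matches the Safety definition, which fits this reading.

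**2. Co-enrolled woman who used the gel.**

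| Source | In Safety? |
|---|---|
| Protocol 9.3 definition | Yes |
| SAP 4.3 definition | Yes |
| SAP Table 2 | No |

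SAP 4.2 lets specific sections override its own general policies. That does not settle this case, because the definition and the table both sit in 4.3.

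**3. Woman enrolled twice.** The first-enrollment rule applies to ITT as well.

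| First enrollment | Second enrollment | In Safety by definition? | In Safety by Table 2? | Second-enrollment data in safety tables? |
|---|---|---|---|---|
| Treated | Treated | Yes | Yes | No |
| Untreated | Treated | Yes | No | No |
| Treated | Untreated | Yes | Yes | No product exposure to report |

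Only the second line breaks the definition. In the first line the woman stays in Safety, but her later adverse events and exposure are left out.

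**4. Which outputs are affected (SAP 6.1 and 6.2)?**

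- *Co-enrolled woman.* She is missing from the adverse event tables 14.3.1.x, the serious adverse event listing 14.3.2.1, the listing of events leading to discontinuation 14.3.2.2, and the Safety-population tables in the 14.3.5 series, including exposure (14.3.5.1) and pregnancy outcomes (14.3.5.16). She remains in the ITT data listings, including Adverse Events 16.2.7.1.
- *Treated second enrollment.* Its data are missing from all tables and listings except the dedicated one, apparently 16.2.3.2. That title names screen failures and second enrollments and does not mention adverse events.

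**5. Scale.** The documents give no number of affected women, so k below is assumed. The planned enrollment of 1349 (Protocol 9.2, SAP 4.11.1) stands in for the number treated.

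Removing k of N women, a of whom had an event with overall proportion p, changes the proportion by (a − kp)/(N − k). This cannot exceed k/(N − k) in size, and it is zero if the excluded women have the same event rate as the others. The chance that at least one excluded woman had a serious event, at an assumed risk q per woman, is 1 − (1 − q)^k.

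| k | k/1349 | Largest possible shift, k/(1349 − k) | q = 0.5% | q = 1% | q = 2% |
|---|---|---|---|---|---|
| 1 | 0.07% | 1/1348 = 0.07 points | 0.5% | 1.0% | 2.0% |
| 5 | 0.37% | 5/1344 = 0.37 points | 2.5% | 4.9% | 9.6% |
| 13 | 0.96% | 13/1336 = 0.97 points | 6.3% | 12.2% | 23.1% |
| 27 | 2.0% | 27/1322 = 2.04 points | 12.7% | 23.8% | 42.0% |

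The largest shift requires an event that every excluded woman had and that was close to absent in the rest. For common events the realistic shift is far smaller. What could be lost is a single serious or rare event.

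**The case against.** The strongest reply is that Table 2 may be deliberate. The SAP presents it as handling rules for special situations, and Protocol 9 leaves further detail to the SAP. A second contraceptive under study could confound the attribution of adverse events, which would be a reason to set such women aside. This stands in part: the documents state no reason, so one cannot conclude that an efficacy rule spread to Safety by accident of the column layout. But Protocol 9.3 has no exception, and the SAP departs from it, and from its own definition, without explanation. Difficulty of attribution is a reason to flag these women rather than leave them out of the summary.

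A reader might also infer that the affected adverse events disappear from the report. For co-enrolled women they do not, because these women stay in ITT and listing 16.2.7.1 is on ITT. Collection and expedited reporting under Protocol 5.4 are untouched. The loss is from the Safety tables and the two event listings on that population.

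A reader might infer that the repeat-enrollment row contradicts the Safety definition as the co-enrollment row does. It does so only for the woman untreated first and treated second. Otherwise it is a gap in reporting.

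Finally, the numbers are likely to be very small, perhaps zero. Inclusion criterion 11 bars other studies, exclusion criterion 18 bars investigational products in the 30 days before consent, and Protocol 4.1.3 provides for rescreening of screen failures but describes no re-enrollment. This stands, and it limits the size of the effect. It does not reconcile the two rules.

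**Conclusion.** The point holds. Table 2 and the Safety definitions give opposite answers for a treated co-enrolled woman, and nothing in either document resolves the conflict. Followed as written, the table omits her from the Safety-population tables and from the listings of serious and discontinuation-related events, while her events remain in the ITT adverse event listing. Separately, data from a treated second enrollment reach only one dedicated listing, whose title does not promise adverse events. In one sequence of enrollments this also breaks the definition.

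The practical effect is small. Efficacy results do not change, and common adverse event percentages would hardly move. The exposure is to individual events: with 5 affected women and an assumed serious-event risk of 0.5% to 2% each, the chance that at least one of them had such an event is 2.5% to 9.6%. Both the count and the risk are assumptions. The documents support no particular count.

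**What to change.** Split the second column of Table 2 into one for Safety and one for MITT and EE.

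| Situation | Safety | MITT and EE |
|---|---|---|
| Screen failures | Excluded | Excluded |
| Not receiving treatment | Excluded | Excluded |
| Enrolled more than once | Included if treated in any enrollment; woman counted once, with adverse events and exposure from every treated enrollment | First enrollment only |
| Enrolled in another interventional contraceptive study | Included if treated | Excluded |

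Amend the sentence below the table so that its exclusion of second enrollments does not apply to Safety-population tables, the serious and discontinuation-related event listings, or listing 16.2.7.1. State that second-enrollment data are linked to the same woman. If co-treatment is thought to cloud attribution, flag these women in the listings.

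The cost is one edited table and one edited sentence, with a small programming change to the Safety flag and to the linking of records. No new data are needed, and the co-enrollment and first-enrollment rules for MITT and EE stay as they are. The change should be made before the population flags are assigned.

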## 4.4 Study Subjects

### 4.4.1 Disposition of Subjects

Subject disposition will be summarized for the ITT population. The following data will be presented:

- The number and percentage of subjects who completed or discontinued prematurely from the study. The number and percentage of subjects who discontinued for each reason will be presented. Data will be summarized for all subjects.
- A listing of subjects that discontinued prematurely from the study. The listing will include information about study center, subject number, age, date of enrollment, last study product use date, number of cycles completed, and reason for discontinuation.
- The number and percentage of all subjects at each scheduled visit.
- The number of subjects who were enrolled at each study center and the number and percentage of subjects who completed or discontinued at each study center will be summarized for all subjects.

The End of Study eCRF will be used to determine who discontinued prematurely from the study.

### 4.4.2 Study Protocol Deviations

The number and percentage of subjects with each violation from protocol inclusion and exclusion criteria will be summarized for all subjects in the ITT population.

## 4.5 Demographic and Pre-Treatment Characteristics

### 4.5.1 Demographic

Subject demographics will be summarized for the ITT, Safety Population, MITT, and EE populations. The summary of demographics will include age, race, ethnicity, height (in), and weight (lb) at baseline, and body mass index (kg/m^2).

A sensitivity analysis will also be performed for the ITT population to detect the differences between completers and non-completers with respect to the following characteristics: age, race, ethnicity, and body mass index (kg/m^2).

### 4.5.2 Gynecological History

The following gynecological history data will be summarized for ITT population:

- The number and percentages of subjects with urinary tract infection (UTI) history (never, not in the past year, once in the past year, twice in the past year, more than twice in the past year, don't know/uncertain);
- The number and percentages of subjects with yeast infection history (never, not in the past year, once in the past year, twice in the past year, more than twice in the past year, don't know/uncertain);

- The number and percentages of subjects with bacterial vaginosis history (never, not in the past year, once in the past year, twice in the past year, more than twice in the past year, don't know/uncertain);
- Summary statistics (sample size, mean, median, SD, minimum, and maximum) for age at menarche;
- Summary statistics (sample size, mean, median, SD, minimum, and maximum) for typical length of menstrual cycle length (in days);
- Summary statistics (sample size, mean, median, SD, minimum, and maximum) for typical duration of menses (in days).

#### **4.5.3 Contraception Use History**

The number and percentage of current users, recent users (used within last 6 months), prior users (used greater than 6 months ago), and never users of the following contraceptive methods reported within the past 1 year from the time of screening will be summarized: male condom, female condom, diaphragm/cervical cap/sponge, oral contraceptive, spermicide, vaginal ring, contraceptive patch, rhythm method (fertility awareness), withdrawal method, progestin or non-hormonal intrauterine device (IUD), injectable contraceptive, contraceptive implant), abstinence, emergency contraception, and other.

This summary will be conducted on the ITT population.

#### **4.5.4 Obstetric History**

Number of pregnancies, number of full-term liveborn deliveries, number of preterm liveborn deliveries, number of living children, number of stillbirth/intrauterine demise > 20 weeks deliveries, number of ectopic pregnancies, number of spontaneous abortions, and number of elective abortions will be summarized descriptively. This summary will be conducted on the ITT population.

#### **4.5.5 Medical History**

Medical history will be coded using MedDRA. The number and percentage of subjects reporting each medical condition will be summarized by body system and preferred term for the ITT population. The number and percentage of subjects reporting any medical history will also be reported.

If subject reports the same medical condition more than once, then that subject is only counted once for the summary of that medical condition.

All medical history will be coded with MedDRA 21.0.

#### **4.5.6 Pre-Treatment Signs and Symptoms**

Pre-treatment signs and symptoms will be coded using MedDRA. The number and percentage of subjects reporting each pre-treatment sign and symptom will be summarized by body system and preferred term for the Safety population. The number and percentage of subjects reporting any pre-treatment signs and symptoms will also be reported.

If subject reports the same pre-treatment sign or symptom more than once, then that subject is only counted once for the summary of that pre-treatment sign or symptom.

All pre-treatment signs and symptoms will be coded with MedDRA 21.0.

#### 4.5.7 Prior and Concomitant Medications

Summaries for prior and concomitant medications will be done for the Safety Population. The following summaries will be performed:

- Prior Medications – Prior medications are considered to be any medication that was stopped prior to the date of enrollment.
- Concomitant Medications – Concomitant medications are considered to be any medication that was taken on or after the date of enrollment.

All medications will be coded to the therapeutic drug classes and generic drug names using the World Health Organization (WHO) Drug classifications. The WHO Drug dictionary version used for this study will be March 2018.

Each summary will give the number and percentage of subjects who took medications that were coded to each generic drug name and therapeutic drug class, as well as the number and percentage of subjects that took any medication at all.

#### 4.6 Treatment Compliance and Study Instruction Departures

Treatment compliance in the Safety Population will be calculated using 5 indices. These 5 indices are the proportion of following acts among all acts of intercourse:

- A. study product only and was used as directed
- B. study product only but product not used as directed
- C. study product and other birth control were used
- D. other birth control only was used
- E. no study drug or birth control was used (i.e. unprotected intercourse)
- F.

For individual subjects, each index will be calculated as:

$$\frac{\text{Total number of acts of intercourse for this index in all cycles}}{\text{Total number of acts of intercourse in all cycles}} \times 100$$

Descriptive statistics will be presented for each index.

Based on the index value, each subject will be in one, and only one, of the following categories for study method only and proper use:

- 0% - 49%
- 50% - 69%
- 70% - 89%
- $\geq 90\%$

Based on the index value, each subject will be in one, and only one, of the following categories for study product only but product not used as directed, study product and other birth control, other birth control only, and no birth control was used:

- 0% - 9%
- 10% - 19%
- 20% - 29%
- 30% - 39%
- 40% - 49%
- $\geq 50\%$

The number and percentage of subjects in each of the above categories will be presented for all subjects.

Various departures from study instructions are as follows:

- Intercourse occurred more than 1 hour but less than or equal to 1.5 hours after application
- Intercourse occurred more than 1.5 hours but less than or equal to 2 hours after application
- Intercourse occurred more than 2 hours but less than or equal to 2.5 hours after application
- Intercourse occurred more than 2.5 hours after application

The departures from study instructions summary will include the number and percent of subjects who report at least one departure from study instructions. The table will also summarize the percentage of acts with departure and categorize them in the following categories:

- 0% - 5%
- 6% - 10%
- 11% - 25%
- 26% - 49%
- $\geq 50\%$

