4.4 Study Drug Use

Eligible subjects will receive study drug to use as their method of contraception while engaging in vaginal sexual intercourse. Study drug will be provided in a prefilled applicator containing 5-grams of drug.

Subjects will be instructed to administer a single pre-filled applicator of study drug intravaginally a maximum of one hour before each episode of vaginal intercourse. Additional applications of study drug should be administered before each additional act of vaginal intercourse regardless of the time of the last application (e.g., if vaginal intercourse occurs more than once in a day). If more than one hour passes before starting intercourse, an additional application of study gel must be applied.

Subjects should be encouraged not to douche during the study; however, if douching does occur, the subject should wait at least six hours after the last act of intercourse and should record the product used as a concomitant medication in the eDiary. Similarly, subjects should be advised not to use lubricants or other vaginal preparations before or during intercourse. If use does occur, it should be recorded in the eDiary and as a concomitant medication.

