## 6 PROPOSED TABLES, FIGURES AND LISTINGS

### 6.1 Proposed Tables and Figures

Number	Title	Population
14.1.1	Subject Disposition	ITT
14.1.2	Listing of Subjects that Discontinued Prematurely	ITT
14.1.3	Number of Subjects at Each Visit	ITT
14.1.4	Number of Subjects at Each Study Site	ITT
14.1.5	Summary of Protocol Deviations	Safety Population
14.1.6	Demographics	ITT
14.1.6.1	Demographics for the Safety Population	Safety Population
14.1.6.2	Demographics for the Modified Intent-to-Treat Population	MITT
14.1.6.3	Demographics for the Efficacy Evaluable Population	EE
14.1.7	Sensitivity Analysis to Dropouts with Respect to Demography	ITT
14.1.8	Gynecological History	ITT
14.1.9	Contraception Use History	ITT
14.1.10	Obstetric History	ITT
14.1.11	Medical History	ITT
14.1.12	Pre-Treatment Signs and Symptoms	ITT
14.1.13	Incidence of Prior Medications	Safety Population
14.1.14	Incidence of Concomitant Medications	Safety Population
14.1.15	Summary of Compliance as Determined by Contraceptive Method	Safety Population
14.1.16	Percent of Coital Acts as Determined by Contraceptive Method	Safety Population
14.1.17	Percent of Coital Acts with Departures from Study Instructions	Safety Population
14.1.18 (figure)	Percentage of Subjects who Completed the Study or Prematurely Discontinued	ITT

Number	Title	Population
14.2.1	Seven-Cycle Cumulative Pregnancy Probabilities for Subjects with Typical-Use	MITT
14.2.2	Sensitivity Analysis with Respect to the Cycle Length	MITT
14.2.3	Sensitivity Analysis with Respect to the Dosing Time with Respect to Sexual Intercourse	MITT
14.2.4	Seven-Cycle Cumulative Pregnancy Probabilities for Subjects with Perfect-Use	EE
14.2.5	Typical-Use Seven-Cycle Based Pearl Rates	MITT
14.2.6	Perfect-Use Seven-Cycle Based Pearl Rates	EE
14.2.7	Summary of Number of Evaluable Cycles	MITT
14.2.8	Summary of Cycles Excluded from Efficacy Evaluable Analysis	MITT
14.2.9 (figure)	Pregnancy Percentage Curves by Kaplan-Meier Method for Subjects with Typical Use	MITT
14.2.10 (figure)	Pregnancy Percentage Curves by Kaplan-Meier Method for Subjects with Perfect-Use	EE
14.3.1.1	Incidence of Adverse Events	Safety
14.3.1.2	Incidence of Serious Adverse Events	Safety
14.3.1.3	Incidence of Adverse Events Leading to Premature Discontinuation	Safety Population
14.3.1.4	Incidence of Adverse Events by Intensity	Safety
14.3.1.5	Incidence of Adverse Events by Relationship to Treatment	Safety

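### SAP 4.6 lists only late intercourse as a departure, so Table 14.1.17 omits a repeat act within one hour without a new applicator and an application made after the act

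*SAP*

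**What the plan says.** Protocol 4.4 (Study Drug Use) sets a time limit: the gel is applied "a maximum of one hour before each episode of vaginal intercourse". It then gives a separate instruction for repeat acts: "Additional applications of study drug should be administered before each additional act of vaginal intercourse regardless of the time of the last application". The second applies whatever the interval since the previous dose.

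SAP 4.6 introduces its list with "Various departures from study instructions are as follows" and gives four items. The first is "Intercourse occurred more than 1 hour but less than or equal to 1.5 hours after application" and the last is "Intercourse occurred more than 2.5 hours after application"; the two between cover the half-hour steps from 1.5 to 2.5 hours. The summary built on this list reports the "number and percent of subjects who report at least one departure from study instructions" and bands the percentage of acts with a departure (0-5%, 6-10%, 11-25%, 26-49%, 50% or more). In SAP 6.1 the output is Table 14.1.17, titled "Percent of Coital Acts with Departures from Study Instructions", in the Safety Population.

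The same section separately classifies all acts by five compliance indices. Index A is "study product only and was used as directed"; B is product alone but not as directed; C and D involve other birth control; E is no product and no other method. The SAP does not define use as directed. It also does not define correct use, on which the EE population (SAP 4.3) and its evaluable cycles (SAP 4.7.2.1) depend.

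**The concern.** The table's title promises departures from the study instructions, but its list covers only one of the two in Protocol 4.4. The uncovered one, a fresh dose for every act, is specific to a product used per act. A woman who omits repeat doses but is otherwise on time would appear in Table 14.1.17 with no departures.

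At stake is the reading of a descriptive table. Someone using it to see how women strayed from the instructions would see late dosing only and would take the total as complete. Index B does not fill the gap, because it pools every kind of incorrect use without type.

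**Working it through.** The plan states no figure to reproduce. The check sets the instructions in Protocol 4.4 against the list in SAP 4.6, case by case.

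| Situation | Under Protocol 4.4 | In the SAP 4.6 list |
|---|---|---|
| Single act, within one hour after application | follows the instructions | no departure |
| Single act, more than one hour after application | breaks the time limit | one of the four bands |
| Second act, more than one hour after the only application | breaks both instructions | one of the four bands, if timed from that application |
| Second act, within one hour of the only application | breaks the repeat-dose instruction | none |
| Application only after the act | breaks the requirement to apply beforehand | none; there is no positive delay to band |

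The last two rows are the gap. For repeat acts it is certain only within one hour of the earlier application, because later ones reach a band if timed from that dose.

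The SAP does not say how an act is linked to an application, so both readings of the fourth row need checking. Timed from the earlier dose, the delay is one hour or less and no band applies. Paired only with its own application, the act has no delay and again no band applies. It is missed either way.

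To show what this can do to one woman's band, assume 20 acts, of which k are repeat acts within one hour without a new applicator, and no other departure:

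- As listed: 0/20 = 0% for any k, band 0-5%.
- With such acts listed: k = 1 gives 1/20 = 5%, band 0-5%; k = 2 gives 2/20 = 10%, band 6-10%; k = 4 gives 4/20 = 20%, band 11-25%.

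Both the 20 acts and the values of k are assumptions. This shows the mechanism and does not estimate its size.

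The data for a fuller list exist: footnote n of the schedule of assessments, in both documents, has women record dates and times of gel use and of sexual activity in the eDiary.

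**The case against.** The strongest reply is that compliance is measured by indices A to E, not by the departures list. Under Protocol 4.4 a repeat act without its own applicator was not as directed, so it belongs in B, or in E if no product is recorded for it. Tables 14.1.15 and 14.1.16 report those indices separately. This stands as a limit on the point. A reader might infer that the plan counts such acts as compliant, but no text places them in index A; because use as directed is undefined, their placement is open.

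Second, Table 14.1.17 is not the only breakdown of use. Indices B to E separate several kinds, and SAP 4.7.3.2 bands acts and pregnancies by dosing time. That is right, but B does not split by error and 4.7.3.2 looks at time alone, so neither is sure to identify an omitted repeat dose.

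Third, the focus on timing fits the exploratory objective on dosing-time deviations (SAP 2.3). That explains the four bands. It does not explain presenting them, in a table about study instructions generally, as the departures from those instructions.

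Fourth, the handling of an application after the act is inferred, since no text covers negative intervals. True, but the four listed items cannot contain one.

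**Conclusion.** The point holds as a minor one. The SAP 4.6 list omits a repeat act within one hour of the only application without a new applicator, and an application made after the act. A programmer following the list would leave both out of Table 14.1.17, which therefore understates departures to the extent that such acts occur. This rests on the wording of the two sections and on no assumed rate. The size of the shortfall cannot be derived, because the documents give no frequency of repeat acts or of omitted repeat doses.

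The consequence is confined to a descriptive Safety Population table. The primary MITT analysis (SAP 4.7.2 and 4.7.2.1) does not draw on the list. A reader might also infer that the perfect-use analysis admits cycles with omitted repeat doses. The documents do not show this: EE requires correct use at every act and simply leaves the term undefined, so an effect there is possible but not demonstrated.

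**What to change.** In SAP 4.6 and Table 14.1.17, add two departure categories derived from the eDiary times:

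1. An act with no new application since the previous act.
2. An application recorded after the act it was for.

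Include both in the count of women with any departure and in the percentage bands. An act meeting more than one category should count once in the percentage.

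State how acts and applications are linked. An application between two acts is the repeat dose for the second and should not be flagged as late for the first. Since category 1 as worded also catches acts with no product at all, say whether acts in indices D and E are included or shown separately.

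Define use as directed (indices A and B) and correct use (EE) against both Protocol 4.4 instructions, using the same flags, so that the three outputs agree.

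The cost is SAP wording and a little extra programming, with no new data collection and no change to any dosing instruction. The reported departure rate may be less favourable. The primary MITT analysis is unaffected.
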